3.2 Secondary endpoints

- 1) Proportion of isCGM stored glucose data < 3.9mmol/L during treatment adjustment.
- 2) Proportion of isCGM stored glucose data < 2.8mmol/L during treatment adjustment.
- 3) Proportion of isCGM stored glucose data > 10.0mmol/L during treatment adjustment.
- 4) Proportion of glucose stored in isCGM > 13.3mmol/L during treatment adjustment.
- 5) The area of glucose in AGP map under the curve of < 10.0mmol/L during treatment adjustment.
- 6) The area of glucose in AGP map under the curve of < 3.9 mmol/L during treatment adjustment.
- 7) Mean value of isCGM stored glucose data during treatment adjustment (MEAN).
- 8) Standard deviation (SD) of isCGM stored glucose data during treatment adjustment.
- 9) Differences between physician approved dose and algorithm recommended dose in intervention group.
- 10) Number of physician overrides in the intervention group.
- 11) In the intervention group, if physician overrides occurred, the proportion of glucose within the range of 3.9mmol/L to 10.0mmol/L within 4 hours after insulin injection.
- 12) In the intervention group, if physician overrides occurred, the sensor glucose level at 4 hours after insulin injection.

4 General considerations

4.1 Population

4.1.1 Sample size

The main study is a randomized controlled trial with noninferiority design. Participants will be assigned 1:1 to either the AP-A arm or the physician arm. We hypothesized that use of the AP-A would not be inferior to physician-guided recommendations in percentage of sensor readings within the target range of 3.9–10 mmol/L. For the sample size calculation, data from the JDRF CGM randomized controlled study and the REPLACE-BG study were used to estimate the properties of the primary endpoint and to define the non-inferiority limit [1][2]. The sample size was calculated using PASS15.0 for non-inferiority analysis, with a margin of 7.5% between arms in a parallel study design with power of 90%, a one-sided significance level of 5% and SD of 13%. Besides, we assume that there is no difference between the two arms in achieving the percentage time of sensor readings within the target range of 3.9–10 mmol/L. The equation for calculating the sample size is as follow [3][4]:

$$n = 2 \frac{(z_{1-\alpha} + z_{1-\beta})^2 S^2}{(\Delta - \delta)^2}$$

In the equation, n is the sample size of each arm, Δ is the non-inferiority margin of the

primary endpoint, δ is the mean difference at which the power is computed, α is the type I error, β is the type II error, and S^2 is the pooled standard deviation of both comparison arms. The resulting analysis showed that 106 subjects were needed for the study. Finally, the study enrolled 119 participants, which met the sample size requirement.

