5.2 Analysis of primary endpoints

For the co-primary endpoint comparisons, the statistical analysis will be performed to evaluate the differences between the two groups for the two primary endpoints during MDI therapy. Specifically, the co-primary endpoints used a stepdown strategy designed to maintain type I error at 5% or less for multiple comparisons. The primary endpoint followed no Gaussian distribution, will be presented as median (interquartile range). The mean (95% confidence intervals, CIs) of between-group differences of the median will be calculated by bootstrap method (1000 replications). For the primary efficacy endpoint, non-inferiority will be established if the lower bound of the CI does not less than the noninferiority margin of -7.5%. For the primary safety endpoint, non-inferiority will be established if the upper bound of the CI does not greater than the non-inferiority margin of 2%, which is selected according to previous reports [1][5]. The per-protocol (PP) sets will be also used for sensitivity analysis.

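### The final SAP states 90% power at one-sided 5%, but its 95% CI rule is a one-sided 2.5% test with about 84% power at 106 patients and 88% at 119

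*Supplement*

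**What the plan says.** Final SAP 4.1.1 gives the design inputs: "with a margin of 7.5% between arms in a parallel study design", and "power of 90%, a one-sided significance level of 5% and SD of 13" percentage points. It adds that "we assume that there is no difference between the two arms", prints a normal-approximation formula for the number per arm, and arrives at 106 patients in total. It ends: "Finally, the study enrolled 119 participants, which met the sample size requirement".

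Final SAP 5.2 sets the decision rule. "The mean (95% confidence intervals, CIs) of between-group differences" of the medians is obtained by bootstrap, and for TIR "non-inferiority will be established if the lower bound of the CI does not less than the noninferiority margin of -7.5" percentage points. The 95% interval is the only one defined there. Section 5.5 sets significance at P < 0.05, two-sided. No 90% interval or one-sided 95% bound appears in the final SAP.

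The protocol and the original SAP of January 2021 carry the same one-sided 5% sizing, and the original SAP also decides on a 95% interval. The final version did not remove the mismatch.

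**The concern.** Comparing the lower limit of a two-sided 95% interval with a margin is a one-sided test at 2.5%. The sample size was calculated for a one-sided test at 5%. The same number of patients has less power under the stricter rule, so the 90% in section 4.1.1 does not describe the test in section 5.2.

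The consequence is one of interpretation. If non-inferiority were not shown, readers would take the result as coming from a test with a 10% chance of missing true equivalence, when the chance was higher. Two significance levels in one plan also leave room for argument, after the results are known, over whether a 90% or a 95% interval was intended.

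**Working it through.** **Inputs**, all from final SAP 4.1.1 unless noted: margin Δ = 7.5; SD S = 13; true difference δ = 0; 1:1 allocation; power 90%; one-sided α = 5%; stated total 106; enrolled 119. Dropout of 5–10% is from the protocol. The decision rule, the lower limit of a 95% CI, is from SAP 5.2 and corresponds to one-sided α = 2.5%.

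**1. The plan's own figure.** The printed formula is n per arm = 2(z₁₋α + z₁₋β)²S²/(Δ − δ)².

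At one-sided 5%: 2 × (1.645 + 1.282)² × 169/56.25 = 51.5, so 52 per arm (104). The noncentral t calculation gives 89.9% power at 52 per arm and 90.4% at 53, so 53 per arm, or 106. The stated figure is right for its stated inputs.

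**2. The number needed under the 95% CI rule.** At one-sided 2.5%: 2 × (1.960 + 1.282)² × 169/56.25 = 63.1, so 64 per arm (128). With the t distribution, 64 per arm gives 89.95% and 65 gives 90.4%, so 65 per arm (130). The 119 enrolled are 9 to 11 fewer. With the protocol's dropout allowance, the enrolment target would have been 135–143 (128/0.95 and 128/0.90) or 137–145 (from 130).

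**3. Power at the actual numbers.** The normal approximation is Φ(7.5/(13√(2/n)) − z₁₋α), with n per arm. For n = 53 the first term is 2.970; for n = 59.5 (119 in total) it is 3.147.

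| Total analysed | One-sided 5%, normal / t | One-sided 2.5%, normal / t |
|---|---|---|
| 106 | 90.7% / 90.4% | 84.4% / 83.7% |
| 119 | 93.3% / 93.1% | 88.2% / 87.7% |
| 113 (119 less 5%) | 92.3% / – | 86.6% / – |
| 107 (119 less 10%) | 91.0% / – | 84.7% / – |

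The type II error under the 95% rule is thus about 16% at 106 and about 12% at 119, against the stated 10%.

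**4. What these figures leave out.** They refer to a difference in means, whereas SAP 5.2 bootstraps a difference in medians because it describes the endpoint as non-Gaussian. As an illustration only, assume normal data with SD 13. The standard error of a median is then about √(π/2) = 1.25 times that of a mean, and at 119 the power becomes Φ(3.147/1.253 − 1.960) = Φ(0.551), about 71%. With skewed data it could be higher or lower.

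The calculation also concerns TIR alone, while the protocol requires both co-primary endpoints to be met. Joint power cannot exceed the power for TIR. It cannot be computed, because the documents give no SD or expected value for time below 3.0 mmol/L.

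**The case against.** Much can be said for the plan. Section 4.1.1 states its significance level openly, and the number follows from it. A reader might infer that the sample size was miscalculated; it was not.

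A reader might also infer that the sentence on 119 patients is false. It directly follows the statement that 106 were needed, and 119 exceeds 106. The sentence is true against the SAP's own figure and falls short only of the 128–130 that the 95% rule implies.

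Nor does the mismatch make non-inferiority easier to claim. The 95% interval is stricter than the level used for sizing, so type I error is not inflated. At the size actually enrolled, and with all randomised participants analysed as section 4.1.2 provides, the means-based shortfall from 90% is about 2 points. Section 4.3 expects little missing data. All of this stands and limits the severity.

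The remaining defence is that a one-sided 5% bound was intended. The text does not support this: it specifies 95% intervals and two-sided testing. The step-down wording, which holds type I error at 5% or less, is satisfied by a 2.5% test as well and defines no other interval. The protocol's 5% randomization test is for the other endpoints. Had a 90% interval been meant, the SAP would still contradict itself.

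**Conclusion.** The final SAP is inconsistent between 4.1.1 and 5.2/5.5, and its stated power is wrong for the test it plans. With its own SD, margin and zero difference, and a comparison of means, the 95% CI rule gives about 84% power at 106 and about 88% at 119 if all are analysed, or roughly 85–87% after 5–10% dropout.

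This is a moderate inconsistency. It would be tempting to call the trial seriously underpowered on the 16% type II error at 106 or the 71% from the median illustration. The documents do not support that: 119 were enrolled rather than 106, and the 71% rests on an assumption of normality that the SAP itself rejects. What can be said is that 88% is not established for the planned bootstrap of medians, and that under the means-based assumptions it is a ceiling once the safety co-primary must also be met.

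**What to change.** Keep the 95% CI rule in 5.2 and correct 4.1.1. Suggested wording:

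> The calculated 106 participants correspond to 90% power at one-sided 5%. Non-inferiority is judged on a 95% CI (one-sided 2.5%). At that level, a comparison of means with the same inputs gives about 84% power for TIR with 106 evaluable participants and about 88% with 119. These figures are means-based approximations. They cover neither the planned bootstrap of medians, for which power may be lower, nor the safety co-primary endpoint. The 119 enrolled exceed the 106 calculated at one-sided 5% but are below the 128–130 implied by the 95% CI rule.

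The last sentence replaces the unqualified statement that the requirement was met. If a figure for the median analysis is wanted, the 71% at 119 may be given with its assumption (normal data, SD 13).

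Do not remove the mismatch by moving to a 90% interval: the data are in, and that would relax the criterion after the fact.

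The cost is wording in the SAP and the trial report, and a less favourable power statement. No further patients and no reanalysis are needed.

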4.1.2 Full analysis set

The major aim of this study is to investigate whether pre-prandial insulin dose adjustments guided by the AP-A under the supervision of physicians is as effective and safe as those guided by physicians alone. The primary endpoint of this study is the percentage of sensor readings within the target range of 3.9–10 mmol/L. Therefore, the full analysis set are defined as all participants who were randomized. The assessment of primary endpoint will be performed based on full analysis set.

4.1.3 Per protocol set

Participants who receive randomization and underwent multiple daily injection therapy, and complete the study according to the study protocol will be included in the per protocol set. The per protocol set is mainly used for sensitivity analysis.

4.2 Covariates analysis

As this is an RCT study, the probability of imbalance in baseline data between the two arms is speculated to be 5% (a minor probability event). Therefore, no multivariate analysis with the adjustment of covariates will be performed to analyze primary endpoint.

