We hypothesized that use of the AP-A would not be inferior to physician-guided recommendations in percentage of sensor readings within the target range of 3.9–10 mmol/L. For the sample size calculation, data from the JDRF CGM randomized controlled study and the REPLACE-BG study were used to estimate the properties of the primary endpoint and to define the non-inferiority limit. The sample size was calculated using PASS 15.0 for non-inferiority analysis, with a margin of 7.5% between arms in a parallel study design with power of 90%, a one-sided significance level of 5% and SD of 13%. The resulting analysis showed that 106 subjects were needed for the study. The sample size was set at 111-116 participants (we rounded it off to about 120), given an estimated 5–10% dropout rate, with randomization in a 1:1 ratio between the two study arms.

Eligible patients were randomly assigned (1:1) to AP-A or physician arm. The randomization was stratified by age and HbA_{1c} at screening using a computer-generated random sequence, and had random block size.

Outcomes

Primary endpoints

The primary endpoint was the non-inferiority for percentage time spent with sensor glucose level in 3.9-10.0 mmol/L (70-180 mg/dL) between the two study arms.

The primary safety endpoint was the percentage time spent with sensor glucose level below 3.0 mmol/L (54 mg/dL).

Secondary endpoints

1. Glycated albumin level at the last visit.
2. Proportion of isCGM stored glucose data < 3.9 mmol/L during treatment adjustment.
3. Proportion of isCGM stored glucose data < 2.8 mmol/L during treatment adjustment.
4. Proportion of isCGM stored glucose data > 10.0 mmol/L during treatment adjustment.
5. Proportion of glucose stored in isCGM > 13.3 mmol/L during treatment adjustment.
6. The area of glucose in AGP map under the curve of < 10.0 mmol/L during treatment adjustment.
7. The area of glucose in AGP map under the curve of < 3.9 mmol/L during treatment adjustment.
8. Mean value of isCGM stored glucose data during treatment adjustment (MEAN).
9. Standard deviation (SD) of isCGM stored glucose data during treatment adjustment.
10. Differences between physician approved dose and algorithm recommended dose in intervention group.
11. Number of physician overrides in the intervention group.
12. In the intervention group, if physician overrides occurred, the proportion of glucose within the range of 3.9 mmol/L to 10.0 mmol/L within 4 hours after insulin injection.

[figure not shown]
Data Analyses

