2.3 Randomization and Blinding

After signing the informed consent forms, the participants will be enrolled according to the inclusion and exclusion criteria. The participants who meet the eligibility criteria will be randomized into two arms. Local investigators randomly allocated participants after their enrolment. The randomization was stratified by age and glycated hemoglobin A1c (HbA1c) at screening using a computer-generated random sequence, and had random block size. The participants and statisticians will be masked to the arm assignment, whereas physicians are not masked due to the nature of the intervention.

3 Study outcomes

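### Randomisation is stratified by age and HbA1c, but the primary analysis leaves both factors out on an imbalance argument that does not bear on precision; the interval stays valid, and precision is lost if either factor predicts time in range

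*Supplement*

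**What the plan says.** Final SAP 2.3: "The randomization was stratified by age and glycated hemoglobin A1c (HbA1c) at screening using a computer-generated random sequence, and had random block size". The protocol names the same two factors under Sample Size and Randomization. Neither document gives cut-points or the number of strata.

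Final SAP 4.2 argues that, because the study is randomised, "the probability of imbalance in baseline data between the two arms is speculated to be 5" per cent, and concludes that "no multivariate analysis with the adjustment of covariates will be performed to analyze primary endpoint".

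Final SAP 5.2 sets the estimator: "The mean (95% confidence intervals, CIs) of between-group differences of the median will be calculated by bootstrap method (1000 replications"). For efficacy, "non-inferiority will be established if the lower bound of the CI does not less than the noninferiority margin of -7.5" per cent. It does not mention resampling within strata.

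The sensitivity analyses named are the per-protocol set (4.1.3, 5.2) and multiple imputation (4.3). Neither uses age or HbA1c, so the stratification factors enter no planned analysis of the primary endpoints.

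**The concern.** The reason given in 4.2 does not support the decision it is given for.

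- **The 5% figure.** It looks like the chance that one covariate differs at p < 0.05 under simple randomisation. It is not the chance of imbalance across a baseline table, and it does not apply to the two stratifiers, whose balance the design enforces.
- **The purpose of adjustment.** Adjusting for a prognostic factor removes the outcome variance that the factor explains, even when the arms are perfectly balanced. Stratified allocation takes between-stratum variation out of the treatment comparison. An analysis that ignores the strata puts that variation back into the interval.

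What is at stake is the width of the interval set against the margin of 7.5 points. If age or HbA1c predicts time in range (TIR), the planned interval is wider than the design requires. Both are recorded at baseline, so using them needs no new data. No baseline sensor value is available instead, because the protocol (Study Procedures) places the sensor after assignment.

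**Working it through.** **Inputs.** Margin 7.5 points, SD 13, true difference 0, one-sided 5%, power 90%, 119 enrolled (final SAP 4.1.1); 1:1 allocation; decision on a 95% CI (5.2). The correlation r of age and HbA1c together with TIR is not in the documents, so it is assumed and shown from 0 to 0.5.

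**Step 1: the plan's own figure.** The formula in 4.1.1 gives n = 2 × (1.645 + 1.282)² × 13² / 7.5² = 51.5, so 52 per arm and 104 in total. The noncentral-t version gives 53 per arm (power 90.4%), which is the stated 106.

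**Step 2: value of adjustment for a difference in means.** Take 59 and 60 patients, all analysed. Residual SD = 13 × √(1 − r²). SE = residual SD × √(1/59 + 1/60). Half-width = t(0.975; 117) × SE. Power is from the noncentral t with noncentrality 7.5/SE, one-sided 2.5%. At r = 0, SE = 2.38, half-width = 1.98 × 2.38 = 4.72 and noncentrality = 3.15. The equivalent sample size is 1/(1 − r²).

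| r | Residual SD | Half-width of 95% CI | Power | Equivalent sample size |
|---|---|---|---|---|
| 0 | 13.00 | 4.72 | 87.7% | 1.00 |
| 0.1 | 12.93 | 4.70 | 88.0% | 1.01 |
| 0.2 | 12.74 | 4.63 | 89.0% | 1.04 |
| 0.3 | 12.40 | 4.50 | 90.5% | 1.10 |
| 0.4 | 11.91 | 4.33 | 92.6% | 1.19 |
| 0.5 | 11.26 | 4.09 | 95.0% | 1.33 |

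The one or two degrees of freedom spent on covariates are ignored. Their cost is negligible: in simulation at r = 0 the half-width was 4.73 adjusted and 4.72 unadjusted.

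**Step 3: the analysis actually planned.** The table is for means, whereas 5.2 plans medians. Trials of 119 were simulated with a normal outcome, four assumed strata and permuted blocks (1,000 trials per setting). The unstratified median bootstrap had a half-width of about 6.0 and power of about 70%, whatever the strata explained. Its coverage was 0.968 when the strata explained nothing, 0.980 at R² = 0.3 and 0.984 at R² = 0.5. Coverage above 95% that tends to rise with R² shows that ignoring prognostic strata makes the interval too wide, not too narrow.

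**Step 4: the same bootstrap resampled within arm and stratum.** If the four strata carry the explained variance, the half-width falls from about 6.0 to about 5.6 at R² = 0.1 and 5.35 at R² = 0.25, with coverage still at least 95%. Part of this is not true gain: resampling in small cells narrows the interval slightly even when the strata are not prognostic. The gain is also smaller if coarse strata capture only part of what age and HbA1c explain.

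**The case against.** A prespecified unadjusted primary analysis is defensible. Leaving out stratifiers does not bias the comparison, and the interval errs on the wide side, which is the safe direction in a non-inferiority trial. This stands in full. A reader might infer from the mismatch between design and analysis that the trial could wrongly declare non-inferiority; the documents and the simulation do not support that.

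The gain is unknown. Entry requires HbA1c of at least 8.0%, which truncates the covariate, and TIR is measured during active inpatient titration. Both could weaken the correlation. At r = 0.1 or 0.2 the gain is only 0.3 or 1.3 points of power. This also stands. It would be tempting to call HbA1c the strongest available predictor, but fasting glucose, C-peptide and diabetes duration are collected too, and nothing in the documents ranks them.

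Most of the planned interval's width comes from the median: under normality, about 6.0 against 4.7 for means. Likewise, power below 90% at r = 0 arises because the sample size used one-sided 5% while the decision uses a 95% CI. Both are separate issues, and a reader should not blame them on the missing covariates.

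One could also stress how often some baseline variable differs by chance: 1 − 0.95^k gives 23% for five independent variables and 40% for ten. That shows the 5% is misread, but it is not a reason to adjust. Many of the listed variables are correlated, and the stratifiers are balanced by design.

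What the objection does not rescue is the rationale in 4.2, or the absence of the stratifiers from every planned analysis of the primary endpoints.

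**Conclusion.** The point holds as one of precision, not of validity. Section 4.2 sets aside the stratification factors for a reason that has no bearing on whether to use them, and 5.2 gives an interval that does not reflect the stratified design. That interval is valid and conservative in this respect.

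The loss depends on a correlation the documents do not report. For a mean difference, using the stratifiers adds nothing at r = 0, 1.3 points of power at r = 0.2, 2.8 points at r = 0.3 (90.5 − 87.7) and 7.3 points at r = 0.5 (95.0 − 87.7). This assumes SD 13, a true difference of 0 and all 119 analysed. For the median bootstrap the corresponding change is a modest narrowing, under an assumed normal outcome and four assumed strata.

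Choosing age and HbA1c as stratifiers suggests that the investigators expected them to matter. It does not show that they do, so a flat statement that the interval is needlessly wide would go beyond the documents.

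**What to change.** Delete the 5% rationale from 4.2 and state how the stratifiers enter the primary TIR analysis. Give the stratum definitions.

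- **If the difference in medians is kept:** resample the bootstrap within arm and randomisation stratum, or use quantile regression on arm, HbA1c and age.
- **If a difference in means is adopted:** say openly that the estimand changes. Fit a linear model on arm, HbA1c and age, with a 95% CI from robust standard errors or a stratified bootstrap.
- **Time below 3.0 mmol/L:** use the stratified bootstrap rather than a linear model, as values probably pile up near zero.
- **Supportive analysis:** keep the unadjusted difference.
- **Timing:** the final SAP already reports 119 enrolled. If the data are unblinded, leave the primary analysis as specified and report the adjusted result as a labelled sensitivity analysis.

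The cost is small: SAP wording, some extra code, and a rule for merging sparse strata, since about 60 patients per arm may leave thin cells. No new data are needed.
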